#### Analyses following one-year follow-up

2. Long-term gain scores (1-year follow-up - baseline)/hours of reported training, for above primary and secondary variables will be compared across Arms.

### EXPLORATORY ANALYSES OF INDIVIDUAL DIFFERENCE PREDICTORS OF GAIN

We will use multiple regression analyses to predict the above post-test and 1 year gain scores on primary and secondary variables from age, education, gender, occupation, expectation for improvement, and study arm.

---

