Age-related perceptual and cognitive declines are associated with difficulties performing everyday tasks required to remain independent [1]. Encouraging improvements in cognitive abilities have been shown for a variety of short-term interventions such as group and individual training on abilities (e.g., the ACTIVE trial; [46]), digital games [6, 23], aerobic exercise [26], and combined treatments [5]). The rationale for these interventions is that they can be expected to support the maintenance of functional independence in older adulthood given the relatively strong relationship between Instrumental Activities of Daily Living (IADLs) performance and cognitive abilities [1], and the range of IADLs required for independence.

There are, however, several limitations to the design and interpretation of broad ability-level cognitive training described above [43]. First, over a century of research on skill acquisition has shown relatively narrow transfer and strong domain specificity for acquired skills [20]. In fact, sometimes a narrow training package may be more effective than training of general abilities, namely broad training, depending on the type of task and target outcome [33]. Given the range of interventions that have shown some efficacy, application of this knowledge to deploying cost-effective population-level interventions requires assessing their *comparative effectiveness*.

Second, relatively few intervention studies have assessed independence using metrics other than cognitive ability measure proxies. For example, many studies have used laboratory task outcomes such as the Useful Field of View (UFOV) test - as a predictor of driving crashes [22] - rather than using performance data from real or simulated driving. Third, practice effects on cognitive measures that are repeated from baseline to post-training test can make it difficult to estimate true change, although increased participant age tends to minimize practice effects and alternate form use can almost eliminate practice effects for some tests [11], though not for all tasks during relatively long periods of intervention [e.g., 37, 38, 39]. Finally, placebo effects, particularly expectation effects, are a serious threat to interpreting intervention studies [8].

[figure not shown]

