This randomized trial was designed to compare the effectiveness of broad and directed (narrow) technology-based training on basic perceptual and cognitive abilities in older adults and on the performance of simulated tasks of daily living. Participants were randomly assigned to four training conditions: (1) a brain game; (2) a video game; (3) IADL training for both fraud avoidance and driving; or (4) an active control condition, involving puzzle solving. This trial seeks to provide guidance not just about what works, but also what works best for a given investment (i.e., time, money) in older adults. The current trial was specifically designed to

address the several methodological limitations mentioned above, including: (1) the development of direct measures of IADL performance, targeting areas related to risks for catastrophic failure (e.g., crashes in driving, losing financial resources to fraud); (2) the use of alternate forms to provide more precise estimates of treatment effects (for both cognitive and IADL measures); (3) inclusion of an active control condition; and (4) measurement of expectation effects (as recommended in [43]). In this paper, we provide a primer to the design of this trial and describe the baseline characteristics of our sample.

Overall design

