This trial is registered on *ClinicalTrials.gov* (Identifier#: NCT03141281). The trial is a single-site randomized controlled trial (RCT), conducted at Florida State University (FSU; Tallahassee, FL), one of four funded sites of the National Institute of Aging Center for Research and Education on Aging and Technology Enhancement (CREATE). Following a telephone screening and baseline assessments, eligible participants were randomized into one of four conditions: (1) Posit Science's BrainHQ; (2) Rise of Nations, a PC-based video game; (3) Instrumental Activities of Daily Living (IADL) training, on both AARP's Driver Safety Course, and a Financial Fraud training course developed for this intervention; (4) active control group, playing a suite of three tasks (i.e., Sudoku, crossword puzzles, and word search). Once participants were assigned to a condition, they received a laptop with specialized software for their condition. Participants received in-lab training designed to encourage familiarity with how to operate a laptop, and the necessary components for their task. Participants were asked to train on their assigned condition for four weeks at home, and return for two scheduled days of post-training assessments, as well as a follow-up assessment at 12 months. The overall study design and contact schedule is summarized in Figure 1. The trial had highly standardized protocols for recruitment, screening, assessment, intervention administration (including manuals sent home with participants), and data transfer from intervention devices. The Institutional Review Board (IRB) at Florida State University, approved the protocol for this trial.

Timeline & Project Flowchart

CERTIFICATION OF ASSESSORS AND INTERVENTIONISTS

All assessors and interventionists who obtain informed consent and/or administer study protocols have already completed CITI training course. In addition, undergraduate and post-bachelor's research assistants have been taught proper procedures and will be directly supervised by the study PI's or someone listed as a co-investigator of research staff in FSU IRB.

SAMPLE RECRUITMENT & RETENTION

Inclusion & Exclusion Criteria

Inclusion

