If pickup: "Hi, my name is _____, I am calling from the Florida State University CREATE Lab. Is _____ there? We are looking for volunteers over the age of 65 to help with our paid research projects.

Do you have a few minutes for us to talk?"

If busy: "When would be a good time for me to call you back?"

- write the day/time in the call back section.
- If they change to not interested, read not interested section below.

If not interested: "Ok, may we keep you on our list for future studies?"

- If no, change status to "don't call"
- If yes, change status to "not interested"

If interested:

"Let me take the next few minutes to tell you about our study. The purpose of this research project is to better understand how training programs are related to cognition. Compensation for this study is 140 dollars.

The main task of this study involves at home laptop software training lasting 1 month. You will be asked to train for roughly 20 hours spread out over a one month period. In addition to at home training, you will have to visit our lab at FSU at a few points throughout the study.

Do you have any questions so far?

To start the study, you will be asked to come for two days of surveys, cognitive tasks and a driving simulator task. On the third day, you will be trained to use the laptop hardware and software. All lab visits will last roughly 1-2 hours.

Similarly, you will be asked to come in for these tasks after completing the home training, and for a 1 year follow up as well.

I know that was a lot of information, do you have any other questions I can answer for you?

Are you interested in participating?"

If not interested: [Thank you for your time, may we call you for future studies?](#)

-If yes: change status to not interested.

-If no: change status to "don't call"

If interested: [Great, do you have about 10 minutes for me to ask some questions to determine your eligibility?](#)

If no: [When would be a good time to call you back?](#)

- write the date and time to call back

If yes: [Before I begin, I want to let you know:](#)

1. All the information that you will be giving me in the next few minutes will be kept confidential.
2. There are no right or wrong answers.
3. If you don't know, can't answer or feel uncomfortable in answering any questions, please let me know.

BATTERY

TAKE-HOME MANUALS

Hardware

Computer User Guide

Contents

△Read this first△	2
△Handle your computer with care△:	2
△Prevent your computer from getting wet△:	2

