COMPLETING A TRAINING SESSION	6
DIARY AFTER TRAINING SESSION	13
SECOND TRAINING SESSION OF THE DAY	14
DESCRIPTION OF DOUBLE DECISION	15
DESCRIPTION OF FREEZE FRAME	17
DESCRIPTION OF TARGET TRACKER	19

About this Quick Guide

The BrainHQ Quick Guide is intended to provide answers to questions about using the BrainHQ software package and about the training schedule we would like you to follow. Should questions arise that are not answered here, please call: [contact].

What is the CREATE Study?

The Center for Research and Education on Aging and Technology Enhancement (CREATE) is conducting a study on cognitive training. This study seeks to measure the possible benefits of brain training games and other types of training on older adults' performance on cognitive tests and everyday tasks such as driving and finance management. The BrainHQ software features a number of games meant to exercise different abilities. These abilities include visual processing speed, alertness and visual discrimination, and the ability to divide one's attention and ignore irrelevant distractors.

[figure not shown]
Over the course of this study you will be asked complete 2 training sessions a day, for 5 days a week for a total of one month (4 weeks). Each training session should last 30 minutes, totaling 1 hour each day.

Logging on to BrainHQ

[figure not shown]
**TASK
1**

1. To load BrainHQ you will need to click on the TASK 1 icon once.

[figure not shown]
2. TASK 1 will load the website and you will be able to access the BrainHQ website as shown in Figure 1.1.

Click the Log In button at the top right of the website. It will open the login window shown in Figure 1.2.

[figure not shown]
3. Enter the email provided for you into the box labeled email.

Email: `[contact]`

Password

4. Enter the password provided for you into the box labeled password.

Email: `[contact]`

••••••••••••••

Log In

[figure not shown]
SET NEW PASSWORD

5. Click on the Log In box after you have entered the email and password.

Completing a Training session

When you log into the BrainHQ website you will be shown a summary of your training session as seen in Figure 2.1. This will provide information on what tasks you need to complete during your training session and will also show you the order of tasks you will complete.

1. This is your training schedule for each training session. Complete 2 training sessions a day, 5 days a week, for a total of one month (4

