- h. Click the FINISHED button to complete a training session.

9. Now that you have completed all the tasks in one training session, please close TASK 1. Move your mouse to the top right of the screen and click the red x. This will close TASK 1 and open your training session Diary.

Diary after training session

1. The diary allows you to record your thoughts and feelings on the previous training session. You will complete a diary after every training session. Do not close TASK 1 until the training session is complete. Shown below in Figure 3.1 is a screen of the diary.

[figure not shown]
The screenshot shows a diary entry form with four rating scales and a text input field. Each scale has seven options: Strongly disagree, Disagree, Somewhat disagree, Neither agree nor disagree, Somewhat agree, Agree, and Strongly agree. The scales are: 1. I found today's session to be enjoyable. 2. I found today's session to be challenging. 3. I found today's session to be frustrating. 4. I was motivated to perform well on today's session. Below these is a question: "During today's session, for how many minutes, did you stop to complete another task? For example, did you complete a household task, or answer a phone call? If you did not stop at any point, please enter 0 in the box below." A text input field contains the value "10". Below that is a question: "Do you have any comments about today's session? WORDS" with a text input field containing "WORD". At the bottom is a green button labeled "Save Diary & Exit".

2. Answer the questions on enjoyability, challenge, frustration, and motivation by clicking on the box with the appropriate answer.
3. For the question “ During today’s session, for how many minutes, did you stop to complete another task” please click on the white box beneath the question and enter a number. Enter 0 if you did not take a break during the task, and if you did take a break during the task or were interrupted from the task enter the number of minutes you were interrupted.
4. If you have any other comments use the white space beneath the question “ Do you have any comments about today’s session” to provide feedback on the training session. If you have no additional comments type NO in the comment box.

5. You do not have to complete both training sessions consecutively. You can split your training sessions into times that are comfortable for you. Please complete 2 training sessions per day and record your thoughts into your diary.

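### Should the SAP compare expectation of improvement across the four arms, given that the protocol calls expectation a serious threat?

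*SAP*

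**What the plan says.** The protocol's background section states that "placebo effects, particularly expectation effects, are a serious threat to interpreting intervention studies". The section that follows lists four responses to the weaknesses of earlier trials. The last two are "inclusion of an active control condition; and (4) measurement of expectation effects (as recommended in [43"].

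In the SAP:

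- The check on random assignment compares the arms on age, education, gender and the outcome variables.
- The efficacy section plans 4-arm by 2-time ANOVAs or ANCOVAs, after training and at one year.
- The comparative effectiveness section compares gain per reported training hour across arms.

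None of these mentions expectation. It enters in the last section, on individual-difference predictors, where multiple regressions predict post-test and one-year gain on "primary and secondary variables from age, education, gender, occupation, expectation for improvement, and study arm".

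On timing, the protocol's Overall design section says: "Following a telephone screening and baseline assessments, eligible participants were randomized into one of four conditions". The telephone script tells recruits, after describing two days of testing: "On the third day, you will be trained to use the laptop hardware and software". The diary described in the Brain HQ handbook does not record expectation: "Answer the questions on enjoyability, challenge, frustration, and motivation by clicking on the box with the appropriate answer".

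**The concern.** An active control guards against expectation effects only so far as its participants expected about as much benefit as those in the other arms. The natural check is to compare expectation ratings by arm, and no sentence in the SAP plans that. Expectation appears only as one of six predictors in a section labelled exploratory, and that section is about individual differences rather than about the arm contrasts.

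The trial aims to say which training works best. If one arm gained more and had also expected more, a reader would want to know before crediting the training. One primary variable, the self-reported IADL task, is the kind of measure most open to expectation. A protocol that names the threat and measures it, followed by an SAP that never sets the measure beside the main results, invites the charge that the safeguard is nominal.

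**Working it through.** The documents give no sample size, expectation scale or effect size, so there is no figure of the plan's to reproduce. The check is what the planned regressions already deliver.

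**1. Coverage.** Counting the variables listed in the SAP's efficacy section:

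| Time | Primary | Secondary | Total |
|---|---|---|---|
| After training | 4 | 5 | 9 |
| One year | 6 | 5 | 11 |
| Both | 10 | 10 | 20 |

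If the two hazard-perception scores (safety, navigation accuracy) are analysed separately, the primary column becomes 5 + 7 = 12 and the grand total 22. The exploratory section covers gain on primary and secondary variables at both times. Each efficacy comparison therefore has a matching regression that contains both expectation and arm.

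**2. Are those regressions about the same contrast?** Let D = follow-up score − baseline score. With two time points, each participant's pair of scores splits into a sum and a difference, and the arm-by-time interaction lies wholly in the difference. For participants measured at both times, the interaction test in the 4 × 2 ANOVA is therefore the one-way test in the model D ~ arm, with 3 numerator degrees of freedom. The exploratory model is

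D ~ arm + expectation + age + education + gender + occupation.

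This is the efficacy contrast with expectation and four personal characteristics added. Assignment cannot alter those four, and randomisation balances them on average, so they do not systematically shift the arm coefficients. Expectation is the one addition that could carry something of the arm.

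One reading needs care. The SAP refers back to gain scores that it has just defined as gain divided by training hours. If the regressions use that ratio, they adjust the comparative effectiveness contrast rather than the arm-by-time one. Either way they give an arm contrast with expectation held fixed, and fitting both is trivial.

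**3. What would a table by arm add?** That depends on when the rating was taken, which the documents supplied do not say.

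- *Before assignment.* Baseline testing precedes randomisation, and software training comes at the third visit. A rating taken only at baseline cannot reflect the arm or its introduction. The table would be one more balance check, and the rating an ordinary covariate.
- *After the training introduction, before home practice.* The table would show whether the arms expected different amounts. Expectation could then be a mediator, so the adjusted arm effect would not isolate bias.
- *At post-test.* The ratings may partly reflect gains already noticed, and differences between arms would be ambiguous.

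Only the middle case makes the table directly informative, and even there it changes no planned test.

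**The case for a change.** The best case for a change is that an adjusted coefficient is not a comparison of expectation. The regressions can show arm effects at equal expectation without showing whether expectation was in fact equal, and they are neither labelled nor placed as a check on the main results. There is also some reason to look. The Brain HQ laboratory script leaves out the driving and money-management aim that the Rise of Nations and IADL scripts state. A table by arm would cost almost nothing.

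Part of this stands. No SAP sentence plans the comparison or states when expectation is rated, and a careful report would give both, with adjusted and unadjusted arm estimates side by side.

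The rest is weaker. The Brain HQ handbook supplies the aim that its laboratory script omits, describing "performance on cognitive tests and everyday tasks such as driving and finance management. The BrainHQ software features a number of games". The recruitment call gives everyone the same neutral purpose: "The purpose of this research project is to better understand how training programs are related to cognition". The IADL script's stress on driving and fraud follows from what the courses teach, and no visible script promises improvement. The control script and the contents of the test battery are not in the text supplied, so nothing can be inferred from them. The protocol promised to measure expectation; it did not promise a test by arm, so the SAP contradicts nothing. Low cost supports good reporting, but it does not show a fault in the plan.

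**Conclusion.** The observation is accurate, but it is a gap that analysts fill sensibly. Expectation sits beside arm in the regressions for all 20 outcome-by-time combinations (22 if the hazard-perception scores are split). What is left over is a descriptive table and a statement of rating time. Neither would change a primary contrast, and no rule in the SAP gives a wrong answer without them. Further nested models of gain on arm, with and without expectation, would largely repeat the planned regressions with fewer covariates, and could be over-read if expectation is a mediator.

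This rests on three assumptions: that expectation was rated in all four arms, as its use as a predictor beside arm implies; that the exploratory section covers every variable it refers back to; and that gain there means either raw gain or gain per hour, both of which are arm contrasts. The documents do not show that expectations differed or that any result is biased, and they give nothing from which to size such an effect.
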